Taking all of the above into account and in keeping with current handling in orthopaedic surgeries where PRP is handled, the Arthrex ACP System for harvesting and preparing PRP under sterile conditions in the OR will be used. This will require the donation of approximately 10cc of patients venous blood drawn prior to the start of the case-in the OR, after patients have been placed under general anesthesia, and under sterile conditions. The Arthrex ACP system will be utilized to prepare the sample and the 3-5ml harvest of supernatant will be utilized to apply the PRP at the end of the case.

The equipment needed: ACP/Double Syringe with Cap, Anticoagulant ACD-A: 50ml, Centrifuge, rotor set, Bucket, Bucket Cap, and counterbalance will be provided by Arthrex.

Research and Design Methods:

- A. Study Design: This is a single-center, prospective, randomized, double-blinded study utilizing patients undergoing ACL reconstruction with autologous bone patellar tendon bone graft harvest under the care of one of two surgeons (SJM or BB) at Surgicare of Manhattan.
- B. Inclusion Criteria:
- Primary ACL Reconstruction
 - Outerbridge \leq 2 at time of surgery
 - Minimum follow up of two years
 - No ligamentous secondary injury
 - Willingness to participate in the study, including follow up at regular intervals and completion of subjective questionnaires
- C. Exclusion Criteria:
- Any previous knee injury
 - Any previous history of patellofemoral pain/anterior knee pain
 - Outerbridge classification 3 or higher
 - Revision ACL
 - Diabetic or smoker
 - Workers compensation patient
 - Any patient with limited English proficiency
 - Pregnant or nursing women
- D. Patient Enrollment: Enrollment will be based on the above inclusion criteria. We plan to enroll approximately 100 patients with 50 randomized to the treatment arm, and 50 to the control. Our power analysis was based upon previous studies on post-operative morbidity in patients undergoing ACL reconstruction with autologous bone patellar tendon bone graft harvest. To establish significance, we need 35 patients per group to detect a 20% difference in anterior knee pain with an $\alpha = .05$ and a power of 80%. Assuming a loss to follow up of up to 30% at two years, adequate sample recruitment was determined to be 50 per group or 100 total. (This calculation and appropriate references are described in this protocol: section I; pg 21)

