- E. Recruitment Procedure: Patients undergoing an ACL reconstruction with autologous BPTB graft harvest will be asked prior to surgery for their participation in this study after considering the inclusion/exclusion criteria. Informed consent will be obtained any time after the patient is booked for surgery (usually 2-3 weeks before surgery) and before the day of surgery (not on the day of surgery). Patients will be blinded to treatment randomization.

F. Data Collection: Data collection will be prospective

- Pre-operative data collection requiring patients to fill out a form will include: the IKDC Demographic Form (see below) which will require approximately 5 minutes of time during a preoperative office visit.

IKDC Demographic Form

IKDC DEMOGRAPHIC FORM

Your Full Name _____

Your Date of Birth _____ / _____ / _____
Day Month Year

Your Social Security Number ____ - ____ - ____ **Your Gender:** **Male** **Female**

Occupation _____

Today's Date _____ / _____ / _____
Day Month Year

The following is a list of common health problems. Please indicate "Yes" or "No" in the first column, and then skip to the next item. If you do have the problem, please indicate in the second column if you receive medications or some other type of treatment for the problem. In the last column, indicate if the problem limits any of your activities.

	Do you have the problem?		Do you receive treatment for it?		Does it limit your activities?	
	Yes	No	Yes	No	Yes	No
Heart disease						
High blood pressure						
Asthma or pulmonary disease						
Diabetes						
Ulcer or stomach disease						
Bowel disease						

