Kidney disease						
Liver disease						
Anemia or other blood disease						
Overweight						
Cancer						
Depression						
Osteoarthritis, degenerative arthritis						
Rheumatoid arthritis						
Back pain						
Lyme disease						
Other medical problem						
Alcoholism						

Page 2 - IKDC DEMOGRAPHIC FORM

1. Do you smoke cigarettes?

- Yes
- No, I quit in the last six months.
- No, I quit more than six months ago.
- No, I have never smoked.

2. Your height centimeters inches

3. Your weight kilograms pounds

4. Your race (indicate all that apply)

- White
- Black or African-American
- Hispanic
- Asian or Pacific Islander
- Native American Indian
- Other

5. How much school have you completed?

- Less than high school
- Graduated from high school

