ΔCrepitus Ant. Compartment	none	moderate	mild pain	>mild pain				
ΔCrepitus Med. Compartment	none	moderate	mild pain	>mild pain				
ΔCrepitus Lat. Compartment	none	moderate	mild pain	>mild pain				
5. Harvest Site Pathology	none	mild	moderate	severe				
6. X-ray Findings								
Med. Joint Space	none	mild	moderate	severe				
Lat. Joint Space	none	mild	moderate	severe				
Patellofemoral	none	mild	moderate	severe				
Ant. Joint Space (sagittal)	none	mild	moderate	severe				
Post. Joint Space (sagittal)	none	mild	moderate	severe				
7. Functional Test								
One Leg Hop (% of opposite side)	≥90%	89 to 76%	75 to 50%	<50%				
**Final Evaluation								

G. Experimental Design

Patients will be randomized using a computer generated randomization table (simple randomization) into one of two treatment arms:

(1) Autologous BPTB ACL reconstruction followed by application of PRP soaked bone chips = Treatment

(2) Autologous BPTB ACL reconstruction = Control

The patient, research personnel and individuals collecting all objective outcome measures will be blinded to the randomization. The operating surgeons (SJM or BB) will evaluate the subjects pre and post operatively but will not contribute any of their objective data collection to the study. Randomization and patient assignments will be done through sequentially numbered opaque sealed envelopes by the circulating nurse in the OR at the time of surgery. The randomization will not be stratified according to surgeon but rather-according to treatment arm. Randomization information will then be recorded and placed into a sealed envelope with the patients' randomization ID and deposited into a locked reception box. This box will only be opened upon completion of the study.

H. Research Procedure

ACL reconstruction

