Will be performed using standard approved surgical technique. The surgeries will be performed by one of two senior surgeons (SJM or BB) and diagnostic arthroscopy will verify the inclusion criteria are met (no additional ligamentous injury, no osteochondral defect, and Outerbridge classification grade 2 or lower). After fixation of the graft and just prior to closure, the senior attending (SJM or BB) and any other research personnel present will leave the room so that application of either PRP soaked cancellous bone chips or non-treated cancellous bone chips to the graft harvest site can be performed in a manner that will maintain blinding. A surgical fellow or resident who will not be present for any portion of the outcomes data collection will do this and therefore, will not compromise the blinding of the study. The Patellar tendon will be closed over the material thus sealing it within the donor site and the wound will be closed using normal guidelines.

PRP Preparation

The PRP will be prepared directly in the operating room prior to the surgical intervention but after the patient has been placed under general anesthesia. The Arthrex ACP Double Syringe system will be used according to their manufacturing guidelines. The blood sample will be obtained by the anesthesiologist at the start of the case, just after the patients have been placed under general anesthesia via the same IV access utilized to administer the anesthesia. The Anesthesiologist will have no role in the data collection or surgical intervention aspect of the study. As the blood will be drawn after patients are asleep, they will remain blinded to their treatment arm and only those in the treatment arm will have blood withdrawn and no additional IV access will be necessary.

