The secondary outcome measures are objective and include radiographic evidence of graft site healing and clinical objective measurements. The primary and secondary outcomes measures for the two groups will be statistically analyzed to evaluate for any differences between the two groups over time using mixed model analysis of variance with Group (PRP vs. no PRP) and the between subjects factor and Time (14d, 1,3,6,12,18 and 24 months post op) as the within subjects factor. Bonferroni corrections will be used for between group or between time pair-wise planned comparisons.

The de-identified data will be entered into an Excel spreadsheet and maintained on a password-protected computer. Once data collection is complete, the principal investigator (SJN) and/or his research assistant (MM) will destroy the master hard copy of identifier codes. Confidentiality of data, data integrity, review of data and study quality will be monitored by the principal investigator and/or his research assistant. Baseline data, demographic data, primary and secondary outcomes will be analyzed using summary statistics, standard deviations and 95% confidence intervals for quantitative data. Qualitative data will be assessed using frequencies and percentages.

J. Informed Consent:

Informed valid written consent will be obtained from all patients at the time of enrollment. This will be in accordance to IRB consent forms

K. Potential Risks & Discomforts:

- a. *Platelet Rich Plasma:* Since PRP is a formulation created entirely from the participants own blood, the complications and risks are extremely low. The anesthesiologist who prepares the blood is highly skilled and will carefully sterilize the skin prior to obtaining the sample. Another side effect that is common is an initial increase in pain and inflammation at the site where the PRP is injected. This occurs because the platelets and blood sample contain natural chemicals that stimulate the immune system. This type of complication is short lived and when it does occur, is treated effectively with pain medication and anti-inflammatory medications, such as Ibuprofen. PRP is not recommended for individuals who have a known bleeding disorder (bleed easily) or are on a medication known to thin the blood such as Coumadin or Lovenox. This makes sense because these patients are more likely to bleed than an individual who has normal bleeding characteristics.

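### Section K.a advises against PRP for people with a known bleeding disorder or on blood-thinning medication, but no eligibility criterion in sections B or C covers them

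*Combined protocol and SAP*

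**What the plan says.** **The caution.** Section K.a (Platelet Rich Plasma) tells the reader that "PRP is not recommended for individuals who have a known bleeding disorder (bleed easily) or are on a medication known to thin the blood". It names Coumadin and Lovenox and explains that such patients are more prone to bleeding. The same paragraph describes the risks of PRP as extremely low.

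**The eligibility rules.** Section D says "Enrollment will be based on the above inclusion criteria". Section E (Recruitment Procedure) adds that patients are approached once the inclusion and exclusion criteria have been considered. The only chronic-disease or lifestyle exclusion in section C is "Diabetic or smoker"; pregnancy and nursing are listed separately. The other exclusions concern the knee, workers compensation status and English proficiency.

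**What is collected before surgery.** The IKDC demographic form in section F has a row for "Anemia or other blood disease" and a catch-all row for other medical problems. For each condition it says: "please indicate in the second column if you receive medications or some other type of treatment for the problem". Section F lists the form as data collection.

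**When assignment happens.** On timing, section E says "Informed consent will be obtained any time after the patient is booked for surgery (usually 2-3 weeks before surgery"), and not on the day itself. Section G places assignment much later, through "sequentially numbered opaque sealed envelopes by the circulating nurse in the OR at the time of surgery".

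**The concern.** The protocol gives a reason not to use its own intervention in a defined group of patients, and then does not turn that reason into an eligibility rule. Someone who screens from sections B and C alone would have no ground to turn away a patient on Coumadin. That patient could be randomised to receive PRP.

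What is at stake is agreement between the safety text and the enrolment rule. The order of events adds a practical reason to settle it early. The envelope is opened in the operating room, and treatment-arm blood is drawn under general anaesthesia. If the problem came to light only then, the patient would already be assigned and could not be asked, and the visible plan does not say what should follow.

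**Working it through.** This is mainly a comparison of texts; the arithmetic is counting.

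**1. Eligibility items against the K.a caution**

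| Source | Items | Covering bleeding disorder or blood thinner |
|---|---|---|
| Section B, inclusion | 5 | 0 |
| Section C, exclusion | 8 | 0 |
| Total | 5 + 8 = 13 | 0 |

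The five inclusion items are primary reconstruction, Outerbridge grade, two-year follow-up, absence of secondary ligament injury, and willingness to participate. The eight exclusions are earlier knee injury, earlier patellofemoral or anterior knee pain, high Outerbridge grade, revision surgery, diabetes or smoking, workers compensation, limited English, and pregnancy or nursing.

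**2. Could the pre-operative form close the gap?** The form has 18 condition rows, from heart disease to alcoholism.

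- One row names blood disease. A known bleeding disorder could be ticked there.
- One row is the catch-all for other medical problems, where a bleeding disorder or the reason for a blood thinner could also appear.
- None of the 18 rows names anticoagulants. The treatment column records whether a condition is treated, not with which drug.

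So 2 of 18 rows are natural places for a relevant answer, and a ticked treatment box elsewhere might prompt a question. No text ties any answer on the form to eligibility.

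**3. Which later steps bear on the question?** Section H says that "diagnostic arthroscopy will verify the inclusion criteria are met (no additional ligamentous injury, no osteochondral defect, and Outerbridge classification grade 2 or lower"). That step is not counted here as a failed screen, for two reasons. It looks at the knee and would not be expected to reveal a bleeding disorder or a drug. It also comes after assignment: only treatment-arm patients have blood drawn, and this is done before the surgeon enters the room, so the envelope must already be open. The withdrawal reasons in section N also apply after assignment and are left out too.

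**4. Effect on sample size.** The plan's own figure, from section I, uses a difference of 2 points, SD 3.0, alpha 0.05 (taken as two-sided) and 80% power:

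n per group = 2 × (1.960 + 0.842)² × 3² / 2² = 2 × 7.85 × 2.25 ≈ 35.3, which rounds up to 36.

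The plan states 35, at which power is 79.6%, so the figure reproduces to within one patient. Allowing for loss, 50 × (1 − 0.30) = 35 per arm. An exclusion applied before randomisation changes who is enrolled, not how many are needed, so 50 and 35 per arm stand.

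**5. What cannot be calculated.** The documents give neither the number of affected patients nor any bleeding rate with PRP-soaked chips. Neither is estimated here.

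**The case against.** The strongest reply is that K.a is generic text about injected PRP. It speaks of the injection site, whereas in this trial PRP-soaked bone chips are placed in the patellar defect and the blood comes from an IV line already in place. Both arms have the same graft harvest and reconstruction. This stands as far as consequence goes: the documents do not show that the soaked chips add bleeding over untreated chips. It does not remove the mismatch, because K.a states the caution without limiting it to injection.

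Second, K.a belongs to the same protocol, so an investigator who reads the whole document has the caution, and routine surgical or anaesthetic work-up may find these patients anyway. Both are fair. But sections D and E point only to the listed criteria, and the protocol neither describes such a work-up nor links it to eligibility.

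Third, the consent pages and some front matter were removed, and a screening statement could sit there. This cannot be excluded. Confidence is therefore high only for the mismatch between K.a and sections B and C, not for the absence of any screen at all.

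A reader might also infer from the form's diabetes and smoking items that it doubles as an eligibility screen from which bleeding was left out. The documents do not support that: no text uses any answer on the form to decide eligibility, and the overlap may be coincidence.

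**Conclusion.** The point holds as a minor inconsistency between the risk section and the eligibility rules: 0 of 13 criteria carry the K.a caution, and the form that might reveal some cases has no consequence attached. It is worth correcting because it affects who may be treated and costs very little.

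A reader might go further and conclude that the trial exposes patients to a demonstrated bleeding hazard, or that the result would be biased or underpowered. The documents support none of these. K.a says only that PRP is not recommended and gives no evidence of excess bleeding from the soaked chips. Assignment is random whichever patients are admitted, and the sample size does not depend on this criterion. Nor should the arthroscopic check or the withdrawal rule be read as further safeguards that failed, since they operate after assignment and serve other purposes.

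The conclusion rests on the visible text and on reading sections B and C as the operative eligibility lists, as sections D and E present them.

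**What to change.** Add one exclusion to section C that takes over K.a's wording: a known bleeding disorder, or being on a medication known to thin the blood, with Coumadin and Lovenox as examples. The term anticoagulant alone could be read more narrowly than K.a.

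Ask about it at booking or consent. Then reconfirm on the day of surgery, before anaesthesia and before the envelope is opened, because a drug may be started or stopped in the intervening weeks. Anyone found ineligible at either check is then never randomised.

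If the investigators judge that the caution does not apply to PRP-soaked bone chips, K.a should say so and why; the two sections would then agree without a new criterion.

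The cost is one line in section C and one question at two existing contacts. The downside is possibly a few fewer eligible patients and slightly slower accrual.

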For each patient in the treatment arm of the study, the anesthesiologist will withdraw 10cc of venous blood prior to the surgeon or research assistants having entered the room. The blood sample will be given to an OR assistant to prepare prior to the start of the case. The 10cc of venous blood will be mixed together with 1 cc of ACD-A (citrate anticoagulant) and centrifuged for 5 min at 1500 rpm. The blood sample will separate into red blood cells and a supernatant “buffy coat” layer containing platelets (PRP) and white blood cells. This Leukocyte rich prp layer will be approximately 3-5cc in volume and will be aspirated into the inner smaller diameter syringe of the double syringe system. Lastly, the PRP phase will be mixed together with .25cc of CaCl₂ and placed within a sterile specimen cup that is covered in aluminum foil so that no one can see what is inside. Once the graft has been harvested, the autologous cancellous bone chips retrieved will be added to the specimen cup by the scrub technician. The PRP and cancellous bone chips will be mixed together in a separate sterile preparatory area of the operating room. They will be left to soak within the concealed container until the end of the case when the chips and PRP will be placed together within the patellar bony defect. A separate member of the staff who is not involved in any of the postoperative data collection measures will do this. Prior to placement of the PRP soaked cancellous chips within the wound and closure, the primary surgeon (SJN or BB) and any personnel present who will also be present during the post operative time frame for outcomes measurements will leave the room.

Concealing the contents of the specimen cup, preparing the PRP and adding it to the specimen cups prior to the presence of any active participant in the study (Senior surgeon or otherwise) entering the room, and adding the prp soaked bone chips to the patellar defect without any active study members in the room ensures blinding.

I. Statistical Analysis/Data Management

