L. Data Safety Monitoring Board: The data safety monitoring plan for this study will involve patient follow-ups and interim analysis. At each follow-up session, the investigator will assess healing of both the donating and recipient sites. If any infections are present, they will be addressed as per standard of care which involves cleaning the area arthroscopically. The investigator will also perform an interim analysis after half of the accrual goal is achieved. At this point, study data will be reviewed by the investigator to ensure patient safety and the continued validity of the study.

M. Potential Benefits:

The participants randomized to receive PRP in this study may directly benefit by having decreased healing time and decreased post operative pain, specifically anterior knee pain common to patients in the postoperative time frame following autologous BPTB reconstruction of their ACL. The study may provide knowledge on the benefits of PRP in graft site healing and patient satisfaction following ACL reconstruction.

N. Discontinuation of Study/Subject Withdrawal

A patient may be withdrawn from the study due to lack of follow up or voluntary withdrawal. The study may also be discontinued at any time depending on the circumstances and any adverse events on the discretion of the investigating personnel and the IRB.

O. Adverse Events

If the patient has any adverse effects from being in the study, they will receive medical care and treatment as needed from the North Shore-Long Island Jewish Health System. However, the patient will be responsible for the costs of such medical treatment, directly or through their medical insurance and/or other forms of medical coverage. No money will be given to the patient. All adverse events will be reported as necessary, per NSLIJ IRB policy.

P. Confidentiality

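### Does the investigator's interim analysis at half accrual open the blind or raise the type I error?

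*Combined protocol and SAP*

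**What the plan says.** Section L (Data Safety Monitoring Board) sets out the look: "The investigator will also perform an interim analysis after half of the accrual goal is achieved". It then gives the purpose: "study data will be reviewed by the investigator to ensure patient safety and the continued validity of the study". With about 100 patients planned, half of accrual is 50.

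Three other sections bear on what the investigator can see and do at that point.

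- Section G (Experimental Design) covers blinding: "The patient, research personnel and individuals collecting all objective outcome measures will be blinded to the randomization". Of the locked box that holds the allocation records it says: "This box will only be opened upon completion of the study". It makes no exception for the interim review.
- Section H (Research Procedure) has the PRP prepared before the senior surgeon or research assistants enter the room. It concludes that "adding the prp soaked bone chips to the patellar defect without any active study members in the room ensures blinding".
- Section I (Statistical Analysis/Data Management) says outcomes will be "statistically analyzed to evaluate for any differences between the two groups over time using mixed model analysis of variance", with visits from 14 days to 24 months. It describes no interim test.

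Section N covers discontinuation: "The study may also be discontinued at any time depending on the circumstances and any adverse events on the discretion of the investigating personnel", together with the IRB. It does not mention the interim review.

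**The concern.** A statistician who reads section L alone sees several warning signs. The look is called an interim analysis. The investigator performs it, although the heading refers to a board. The data to be reviewed are not specified, and no significance level, boundary or stopping rule is given. Section N leaves discontinuation to discretion.

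If the look compared the arms, two things would be at stake. The investigator would learn the allocation or the emerging effect while half the patients were still to be enrolled, and the main outcomes are patient-reported pain scores. A second unadjusted test at 0.05 would also push the false-positive rate above the 5% on which the sample size rests.

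**Working it through.** **1. The plan's own figure.** Section I uses a difference of 2.0 VAS points, SD 3.0, alpha 0.05 and power 80%. For two means with a two-sided test,

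n per group = 2 × [SD × (1.960 + 0.842) / difference]² = 2 × [3 × 2.802 / 2]² = 35.3.

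The plan states 35, which gives 79.6% power by the same normal formula. Allowing for 30% loss, 35 / 0.70 = 50 per group, or 100 in total. The figure reproduces. It assumes one test at 0.05, so an extra between-arm test would matter.

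**2. What a by-arm test would need, set against the plan.**

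| Needed for a by-arm efficacy look | What the plan provides |
|---|---|
| Allocation available at 50 patients | Section G: box closed until completion, no exception |
| A reviewer who may be unblinded | Section G: research personnel blinded; section H: study members absent when PRP is applied |
| An interim endpoint, test and boundary | Section I: none |
| Efficacy as a purpose | Section L: safety and continued validity only |

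None of the four is met, and no section conflicts with a pooled reading.

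**3. Error under the plan as written.** A pooled review has no rejection region, so the null hypothesis can be rejected only at the final analysis. Suppose the pooled data led to discontinuation. If PRP has no effect on anything reviewed, pooled outcomes carry no information about the randomized allocation, so a later between-arm test keeps its level. The interim look adds 0 to the type I error.

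**4. Size of the hypothetical problem.** Suppose instead that the arms were compared at 50 patients with |Z₁| > 1.96, that the trial could end there with a claim, and that the final test were also at 1.96. The two statistics are bivariate normal with correlation √t, where t is the information fraction, and

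overall error = 1 − P(|Z₁| < 1.96 and |Z₂| < 1.96).

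| t | 0.5 | 0.3 | 0.2 | 0.1 |
|---|---|---|---|---|
| Error | 8.3% | 8.9% | 9.2% | 9.5% |

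The documents do not fix t. As an illustration, assume even accrual over 24 months, enrolment taken as surgery, no losses and an equal within-patient correlation of 0.5. At the 50th enrolment 48, 45, 37 and 25 patients have reached the 14-day, 1-, 3- and 6-month visits. That is 155 of 700 readings (22.1%), none of them at 24 months. For a group effect averaged over visits, a patient with k readings contributes k / (1 + (k − 1) × 0.5):

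- 25 patients with four readings: 25 × 1.600 = 40.0
- 12 with three: 12 × 1.500 = 18.0
- 8 with two: 8 × 1.333 = 10.7
- 3 with one: 3 × 1.000 = 3.0

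The sum is 71.7. Full information is 100 × 7 / (1 + 6 × 0.5) = 175, so t = 71.7 / 175 = 0.41 and the error is 8.6%. With accrual over 12 to 48 months and correlation 0.3 to 0.7, t runs from 0.31 to 0.47 and the error from 8.9% down to 8.4%. If only a result favouring PRP could stop the trial, the error is 7.0% down to 6.7%.

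These figures describe a procedure that the plan does not contain.

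**The case for a change.** The strongest case for the concern is that the pooled reading is inferred and not written down. Section G never mentions the interim. The box may not be the only route to allocation: section G also refers to a computer-generated table without naming who keeps it, and section H has blood drawn only in the PRP arm. Section N's wording on circumstances is broad and does not exclude stopping for efficacy or futility. A pooled review cannot compare harms between arms, although safety is the review's stated purpose.

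Some of this stands. Section L is silent on pooling, the table's custodian is not named, and no independent board is described despite the heading. But these are unwritten details, and none of them plans or permits a between-arm test. Section G's rule on the box is unconditional. Section H places the blood draw before the surgeon or research assistants enter. Discretion under section N gives no efficacy claim when the investigator holds no between-arm result. Safety can still be followed patient by patient: section L has healing and infection assessed at each follow-up, and the IKDC knee examination form grades "Harvest Site Pathology". Whether harms should also be reviewed by arm, and by whom, is a separate question of safety oversight that does not touch alpha or the blind.

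A further caution is fair. The absence of inflation from the interim look does not show that the whole analysis holds 5%. Section I covers several outcomes and seven visits, and states Bonferroni correction only for pairwise comparisons between groups or times. That is a different matter from the interim.

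**Conclusion.** The concern does not hold. Read together, sections G, H, I and L give a blinded review at 50 patients for safety and study validity, with no between-arm test. The look adds nothing to the type I error and does not open the blind, and the stated 35 per group (50 after losses) needs no adjustment for it. The 8.3% to 9.5% range applies only if allocation were released, the arms were tested at an unadjusted 0.05, and the trial could end on the result with a claim. The plan provides for none of these.

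The conclusion rests on section G being followed: the box stays shut and the randomization table is not used at the interim. A sentence in section L saying that the review is pooled would spare the reader from combining sections, but it would change no analysis and no result.
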